Appendix 12. 2016 WHO Classification of Myelodysplastic Syndromes

Name	Dysplastic lineages	Cytopenias*	Ring sideroblasts as % of marrow erythroid elements	BM and PB blasts	Cytogenetics by conventional karyotype analysis
MDS with single lineage dysplasia (MDS-SLD)	1	1 or 2	<15%/<5%†	BM <5%, PB <1%, no Auer rods	Any, unless fulfills all criteria for MDS with isolated del(5q)
MDS with multilineage dysplasia (MDS-MLD)	2 or 3	1-3	<15%/<5%†	BM <5%, PB <1%, no Auer rods	Any, unless fulfills all criteria for MDS with isolated del(5q)
MDS with ring sideroblasts (MDS-RS)					
MDS-RS with single lineage dysplasia (MDS-RS-SLD)	1	1 or 2	≥15%/≥5%†	BM <5%, PB <1%, no Auer rods	Any, unless fulfills all criteria for MDS with isolated del(5q)
MDS-RS with multilineage dysplasia (MDS-RS-MLD)	2 or 3	1-3	≥15%/≥5%†	BM <5%, PB <1%, no Auer rods	Any, unless fulfills all criteria for MDS with isolated del(5q)
MDS with isolated del(5q)	1-3	1-2	None or any	BM <5%, PB <1%, no Auer rods	del(5q) alone or with 1 additional abnormality except -7 or del(7q)
MDS with excess blasts (MDS-EB)					
MDS-EB-1	0-3	1-3	None or any	BM 5%-9% or PB 2%-4%, no Auer rods	Any
MDS-EB-2	0-3	1-3	None or any	BM 10%-19% or PB 5%-19% or Auer rods	Any
MDS, unclassifiable (MDS-U)					
with 1% blood blasts	1-3	1-3	None or any	BM <5%, PB = 1%,‡ no Auer rods	Any
with single lineage dysplasia and pancytopenia	1	3	None or any	BM <5%, PB <1%, no Auer rods	Any
based on defining cytogenetic abnormality	0	1-3	<15%§	BM <5%, PB <1%, no Auer rods	MDS-defining abnormality
Refractory cytopenia of childhood	1-3	1-3	None	BM <5%, PB <2%	Any

*Cytopenias defined as: hemoglobin, <10 g/dL; platelet count, <100 × 10⁹/L; and absolute neutrophil count, <1.8 × 10⁹/L. Rarely, MDS may present with mild anemia or thrombocytopenia above these levels. PB monocytes must be <1 × 10⁹/L

†If SF3B1 mutation is present.

‡One percent PB blasts must be recorded on at least 2 separate occasions.

§Cases with ≥15% ring sideroblasts by definition have significant erythroid dysplasia, and are classified as MDS-RS-SLD.

CCI [REDACTED]
[REDACTED]
[REDACTED]
[REDACTED]

CCI [Redacted]

CCI [Redacted]

CCI [Redacted]

CCI [Redacted]

CCI

A horizontal black redaction bar covering a line of text.

CCI

A large rectangular black redaction block covering multiple lines of text.

[figure not shown]
CCI

A very large rectangular black redaction block covering the majority of the page's content.

[figure not shown]
CCI

A horizontal black redaction bar covering a line of text.

CCI

CCI

Appendix 16. 2017 ELN AML Risk Stratification by Genetics

Risk category*	Genetic abnormality
Favorable	t(8;21)(q22;q22.1); RUNX1-RUNX1T1 inv(16)(p13.1q22) or t(16;16)(p13.1;q22); CBFB-MYH11 Mutated NPM1 without FLT3-ITD or with FLT3-ITD ^{low} † Biallelic mutated CEBPA
Intermediate	Mutated NPM1 and FLT3-ITD ^{high} ‡ Wild-type NPM1 without FLT3-ITD or with FLT3-ITD ^{low} † (without adverse-risk genetic lesions) t(9;11)(p21.3;q23.3); MLL3-KMT2A ‡ Cytogenetic abnormalities not classified as favorable or adverse
Adverse	t(6;9)(p23;q34.1); DEK-NUP214 t(v;11q23.3); KMT2A rearranged t(9;22)(q34.1;q11.2); BCR-ABL1 inv(3)(q21.3q26.2) or t(3;3)(q21.3;q26.2); GATA2,MECOM(EVI1) -5 or del(5q); -7; -17/abn(17p) Complex karyotype,§ monosomal karyotypell Wild-type NPM1 and FLT3-ITD ^{high} ‡ Mutated RUNX1 ¶ Mutated ASXL1 ¶ Mutated TP53 #

Frequencies, response rates, and outcome measures should be reported by risk category, and, if sufficient numbers are available, by specific genetic lesions indicated.

*Prognostic impact of a marker is treatment-dependent and may change with new therapies.

†Low, low allelic ratio (<0.5); high, high allelic ratio (≥0.5); semiquantitative assessment of *FLT3-ITD* allelic ratio (using DNA fragment analysis) is determined as ratio of the area under the curve “*FLT3-ITD*” divided by area under the curve “*FLT3-wild type*”; recent studies indicate that AML with *NPM1* mutation and *FLT3-ITD* low allelic ratio may also have a more favorable prognosis and patients should not routinely be assigned to allogeneic HCT.^{57-59,77}

‡The presence of t(9;11)(p21.3;q23.3) takes precedence over rare, concurrent adverse-risk gene mutations.

§Three or more unrelated chromosome abnormalities in the absence of 1 of the WHO-designated recurring translocations or inversions, that is, t(8;21), inv(16) or t(16;16), t(9;11), t(v;11)(v;q23.3), t(6;9), inv(3) or t(3;3); AML with *BCR-ABL1*.

llDefined by the presence of 1 single monosomy (excluding loss of X or Y) in association with at least 1 additional monosomy or structural chromosome abnormality (excluding core-binding factor AML).¹¹⁶

¶These markers should not be used as an adverse prognostic marker if they co-occur with favorable-risk AML subtypes.

#*TP53* mutations are significantly associated with AML with complex and monosomal karyotype.^{37,66-69}

From: Döhner H, Estey E, Grimwade D, et al. Diagnosis and management of AML in adults: 2017 ELN recommendations from an international expert panel. *Blood* 2017;129(4): 424-47.⁴²

Appendix 17. 2016 WHO Classification of Myeloid Neoplasms and Acute Leukemia

Myeloproliferative neoplasms (MPN)

Chronic myeloid leukemia (CML), *BCR-ABL1*⁺

Chronic neutrophilic leukemia (CNL)

Polycythemia vera (PV)

Primary myelofibrosis (PMF)

PMF, prefibrotic/early stage

PMF, overt fibrotic stage

Essential thrombocythemia (ET)

Chronic eosinophilic leukemia, not otherwise specified (NOS)

MPN, unclassifiable

Mastocytosis

Myeloid/lymphoid neoplasms with eosinophilia and rearrangement of *PDGFRA*, *PDGFRB*, or *FGFR1*, or with *PCM1-JAK2*

Myeloid/lymphoid neoplasms with *PDGFRA* rearrangement

Myeloid/lymphoid neoplasms with *PDGFRB* rearrangement

Myeloid/lymphoid neoplasms with *FGFR1* rearrangement

Provisional entity: Myeloid/lymphoid neoplasms with PCM1-JAK2

Myelodysplastic/myeloproliferative neoplasms (MDS/MPN)

Chronic myelomonocytic leukemia (CMML)

Atypical chronic myeloid leukemia (aCML), *BCR-ABL1*⁻

Juvenile myelomonocytic leukemia (JMML)

MDS/MPN with ring sideroblasts and thrombocytosis (MDS/MPN-RS-T)

MDS/MPN, unclassifiable

Myelodysplastic syndromes (MDS)

MDS with single lineage dysplasia

MDS with ring sideroblasts (MDS-RS)

MDS-RS and single lineage dysplasia

MDS-RS and multilineage dysplasia

MDS with multilineage dysplasia

MDS with excess blasts

MDS with isolated del(5q)

MDS, unclassifiable

Provisional entity: Refractory cytopenia of childhood

Myeloid neoplasms with germ line predisposition

Acute myeloid leukemia (AML) and related neoplasms

AML with recurrent genetic abnormalities

AML with t(8;21)(q22;q22.1);*RUNX1-RUNX1T1*

AML with inv(16)(p13.1q22) or t(16;16)(p13.1;q22);*CBFB-MYH11*

APL with *PML-RARA*

AML with t(9;11)(p21.3;q23.3);*MLLT3-KMT2A*

AML with t(6;9)(p23;q34.1);*DEK-NUP214*

AML with inv(3)(q21.3q26.2) or t(3;3)(q21.3;q26.2); *GATA2, MECOM*

AML (megakaryoblastic) with t(1;22)(p13.3;q13.3);*RBM15-MKL1*

Provisional entity: AML with BCR-ABL1

AML with mutated *NPM1*

AML with biallelic mutations of *CEBPA*

Provisional entity: AML with mutated RUNX1

AML with myelodysplasia-related changes

Therapy-related myeloid neoplasms

AML, NOS

AML with minimal differentiation

AML without maturation

AML with maturation

Acute myelomonocytic leukemia

Acute monoblastic/monocytic leukemia

Pure erythroid leukemia

Acute megakaryoblastic leukemia

Acute basophilic leukemia

Acute panmyelosis with myelofibrosis

Myeloid sarcoma

Myeloid proliferations related to Down syndrome

Transient abnormal myelopoiesis (TAM)

Myeloid leukemia associated with Down syndrome

Blastic plasmacytoid dendritic cell neoplasm

Acute leukemias of ambiguous lineage

Acute undifferentiated leukemia

Mixed phenotype acute leukemia (MPAL) with t(9;22)(q34.1;q11.2); *BCR-ABL1*

MPAL with t(v;11q23.3); *KMT2A* rearranged

MPAL, B/myeloid, NOS

MPAL, T/myeloid, NOS

B-lymphoblastic leukemia/lymphoma

B-lymphoblastic leukemia/lymphoma, NOS

B-lymphoblastic leukemia/lymphoma with recurrent genetic abnormalities

B-lymphoblastic leukemia/lymphoma with t(9;22)(q34.1;q11.2); *BCR-ABL1*

B-lymphoblastic leukemia/lymphoma with t(v;11q23.3); *KMT2A* rearranged

B-lymphoblastic leukemia/lymphoma with t(12;21)(p13.2;q22.1); *ETV6-RUNX1*

B-lymphoblastic leukemia/lymphoma with hyperdiploidy

B-lymphoblastic leukemia/lymphoma with hypodiploidy

B-lymphoblastic leukemia/lymphoma with t(5;14)(q31.1;q32.3) *IL3-IGH*

B-lymphoblastic leukemia/lymphoma with t(1;19)(q23;p13.3); *TCF3-PBX1*

Provisional entity: B-lymphoblastic leukemia/lymphoma, BCR-ABL1-like

Provisional entity: B-lymphoblastic leukemia/lymphoma with iAMP21

T-lymphoblastic leukemia/lymphoma

Provisional entity: Early T-cell precursor lymphoblastic leukemia

Provisional entity: Natural killer (NK) cell lymphoblastic leukemia/lymphoma

Appendix 18. France Appendix

This appendix applies to study sites located in France.

1. GCP Training

Prior to enrollment of any subjects, the investigator and any sub-investigators will complete the Pfizer-provided Good Clinical Practice training course (“Pfizer GCP Training”) or training deemed equivalent by Pfizer. Any investigators who later join the study will complete the Pfizer GCP Training or equivalent before performing study-related duties. For studies of applicable duration, the investigator and sub-investigators will complete Pfizer GCP Training or equivalent every three years during the term of the study, or more often if there are significant changes to the ICH GCP guidelines or course materials.

2. Investigational Product

No subjects or third-party payers will be charged for investigational product.

3. Inspections

The investigator(s) will notify Pfizer or its service provider immediately of any regulatory inspection notification in relation to the study. Furthermore, the investigator will cooperate with Pfizer or its service provider to prepare the study site for the inspection and will allow Pfizer or its service provider (if not prohibited by law) to be present during the inspection. The study site and investigator will promptly resolve any discrepancies that are identified between the study data and the subject's medical records. The investigator will promptly provide copies of the inspection findings to Pfizer or its service provider. Before response submission to the regulatory authorities, the investigator will provide Pfizer or its service provider with an opportunity to review and comment on responses to any such findings.

1. AMENDMENTS FROM PREVIOUS VERSION(S)

This amendment of the Statistical Analysis Plan was finalized following Protocol Amendment #5 dated August 22, 2017 and Amendment #6 dated Nov 27, 2017. The main changes relevant to this analysis plan are as follows:

Randomized Phase 2 component is removed from the protocol in amendment #5. Expansion component with two cohorts, MDS and AML, are added into the protocol. Bayesian decision rule is used in the expansion component of the study for potential early stopping.

In amendment 6, a set of safety stopping criteria are added. CRh as one of the secondary endpoints for AML patients. CCI as exploratory endpoints are added. PRO endpoint PGIS has been updated from a 7-point Likert scale to a 4-point Likert scale. All of these additions and changes were per FDA request.

2. INTRODUCTION

PF-04449913 is a novel small molecule inhibitor of the Sonic Hedgehog (Hh) Pathway which is currently under development for the treatment of hematologic malignancies and solid tumors.

This multi-center open-label Phase 1b study is designed to evaluate the safety, efficacy, pharmacokinetics (PK), and pharmacodynamics (PD) of PF-04449913 when combined with azacitidine in patients with previously untreated Higher-Risk Myelodysplastic Syndrome (MDS), Acute Myeloid Leukemia (AML), and Chronic Myelomonocytic Leukemia (CMML). This Phase 1b study includes two components: (a) a safety lead-in cohort (LIC) and (b) an expansion phase with two cohorts.

2.1. Study Design

This multi-center, open-label Phase 1b study is designed to evaluate the safety, efficacy, PK, and PD of PF-04449913 when combined with azacitidine in patients with previously untreated Higher-Risk MDS, AML, and CMML. The Phase 1b study includes two components: (a) a safety LIC, and (b) an expansion phase with two cohorts.

[figure not shown]
2.1.1. Safety Lead-In Cohort (LIC)

As of 23 September 2015, a safety LIC of 12 patients with previously untreated Intermediate-2 or High-Risk MDS per IPSS (n=7), AML with 20-30% blasts and multi-lineage dysplasia (n=3), erythroleukemia (n=1), and CMML (n=1) were enrolled and received open-label treatment with PF-04449913 at a starting dose of 100 mg given orally once/day in combination with azacitidine at the starting dose of 75 mg/m²/day given SC for 7 consecutive days every 28 days. An evaluation of the DDI potential between PF-04449913 and azacitidine was performed. An internal safety review team reviewed the LIC data after each patient had received at least 4 weeks of treatment and determined that the safety profile of PF-04449913 in combination with azacitidine in the defined population was consistent with what is expected for PF-04449913 or azacitidine alone with no unexpected toxicities identified, therefore the combination was deemed acceptable to proceed to the next phase of development.

2.1.2. Expansion

Patients with previously untreated Intermediate, High, or Very High risk MDS per IPSS-R (n=30) or patients with AML who are not candidates for intensive chemotherapy (n=30) will receive PF-04449913 100 mg orally once/day in combination with azacitidine 75 mg/m²/day given by SC or IV for 7 days (±3 days) every 28 days.

Figure 1. Schematic of Study Design

*MDS patients enrolled in the Safety Lead-In component must have Intermediate-2 or High-Risk disease according to IPSS.

**MDS patients enrolled in the Expansion component must have Intermediate, High, or Very High risk disease according to IPSS-R.

2.2. Study Objectives

2.2.1. Objectives for the Safety LIC

Primary Objective

- To assess the safety and tolerability of PF-04449913 when administered in combination with azacitidine in patients with previously untreated Intermediate-2 or High-Risk MDS, AML with 20-30% blasts and multi-lineage dysplasia, and CMML.

Secondary Objectives

- To assess the Response Rate (RR);
- To assess other clinical efficacy measures;
- To characterize the PK of PF-04449913 and azacitidine alone and in combination;

- *To characterize the effects of PF-04449913 in combination with azacitidine on QTc interval.*

CCI [REDACTED]

- █ [REDACTED]
- █ [REDACTED]
- █ [REDACTED]

2.2.2. Objectives for the Expansion

Primary Objective

- *To determine the complete remission (CR) rate of PF-04449913 when administered in combination with azacitidine in patients with previously untreated Intermediate, High, or Very High risk MDS and AML not suitable for intensive chemotherapy.*

Secondary Objectives

- *To assess overall survival (OS);*
- *To assess other clinical efficacy measures;*
- *To assess duration of CR;*
- *To assess time to CR;*
- *To evaluate the overall safety profile of PF-04449913 + azacitidine;*
- *To evaluate the pharmacokinetic parameters of PF-04449913;*
- *To characterize any effects of PF-04449913 + azacitidine on QTc interval.*

CCI [REDACTED]

- █ [REDACTED]
- █ [REDACTED]
- █ [REDACTED]

3. INTERIM ANALYSES, FINAL ANALYSES AND UNBLINDING

Phase 1b Tolerability Evaluation

Note that safety information from the Phase 1b safety LIC of the study will be reviewed by an internal safety review team to determine the safety and tolerability profile of the combination when all patients in the Phase 1b component have been followed for at least 4 weeks.

Interim Futility Analysis

A Bayesian decision rule will be used to continuously monitor CR rate without holding enrollment in the expansion component to allow early stopping of the study for futility. The decision rule is to stop enrollment for a specific expansion cohort if the posterior probability of the CR rate in study treatment is no more than 0.2 higher than historical azacitidine is greater than 95% in an expansion cohort, i.e., $\Pr(\text{glasdegib+Aza response} < \text{historical Aza response} + 0.2) > 0.95$. The prior distribution assumptions for the Bayesian model are as follow: for MDS cohort, we assume a prior distribution of Beta(1,6) for the study treatment (based on data from MDS patients accumulated in the safety LIC [1 out of 7 MDS patients achieved CR]), and a prior distribution of Beta(15,75) by discounting historical CR rate by half (AZA 001 trial); for the AML cohort, a prior distribution of Beta(4,4) for the study treatment (based on pooled data on AML patients from the B1371003 study [1 out of 4 AML patients achieved CR] and the LIC [3 out of 4 AML patients achieved CR]), and a prior distribution of Beta(23.5,97) by discounting historical CR rate by half. The Multic Lean software (Version 2.1.0) developed by MD Anderson Cancer Center is used (https://biostatistics.mdanderson.org/softwaredownload/SingleSoftware.aspx?Software_Id=12), which properly models variability in historical control that is more often than not ignored. Stopping for toxicity is not modeled.

The Bayesian decision rule applies once the minimum number of patients (i.e., 10) in each expansion cohort has achieved the required follow-up duration (i.e., 28 weeks for the expansion MDS cohort and 24 weeks for the expansion AML cohort). The enrollment to the respective expansion cohort will be stopped if the minimum number of responders in that expansion cohort is not achieved (for expansion MDS cohort, and for expansion AML cohort in Protocol Section 3.3). For instance, if there are no more than 4 responders in the first 17 patients who have achieved 28 weeks follow-up, the enrollment into the expansion MDS cohort should be stopped for futility.

Safety Stopping Analyses

Analysis of specific safety criteria will be performed to evaluate stopping enrollment for a specific cohort when there is at least 70% probability that the toxicity rate of any of the predefined safety events of interest (Protocol Section 3.3) in that cohort is above 25%. The safety stopping criteria will be applied separately within each cohort (AML or MDS) starting when at least 10 patients have completed the required follow-up period (28/24 weeks

for MDS/AML respectively) and applied continuously afterwards. Enrollment will continue unless the stopping boundary is crossed (Table 10 in Section 3.3 of the Protocol). Patients who have completed the required follow-up period or patients who have experienced any pre-defined safety events of interest within the required follow-up period will be included in the safety decision making. The same stopping criteria will be used for the AML and MDS cohorts; however, the two cohorts will be analyzed independently.

Final Analysis

The timing of the final analysis is determined by the expansion component of the study. The final analyses for MDS cohorts will be performed after all patients in the expansion MDS cohort have been followed for at least 28 weeks (to allow for confirmation of response per IWG 2006). The final analyses for the AML cohort will be performed after all patients in this cohort have been followed for at least 24 weeks.

Unblinding

The safety LIC and expansion component of the study are open-label and unblinding does not apply.

4. HYPOTHESES AND DECISION RULES

4.1. Statistical Hypotheses

There are no formal statistical hypotheses for the Phase 1b safety LIC and expansion component of the study.

4.2. Statistical Decision Rules

The decision rule at the interim analysis is described in [Section 3](#).

5. ANALYSIS SETS

5.1. Full Analysis Set (FAS)

The full analysis set will include all enrolled patients in the respective cohort (LIC, expansion MDS, and expansion AML cohort separately), who received at least one dose of any study treatment (PF-04449913 or azacitidine). This will be the primary analysis population for evaluating efficacy endpoints and patient characteristics.

5.2. Safety Analysis Set

The safety analysis set will include all patients in the respective cohort (LIC, expansion MDS, and expansion AML cohort separately) who receive at least one dose of any study treatment (PF-04449913, or azacitidine). It will be the primary analysis population for evaluating treatment administration/compliance and safety endpoints.

5.3. PK Analysis Set

The PK concentration analysis set is defined as all patients who are treated and who have at least 1 value of analyte concentration of PF-04449913 or azacitidine available. The PK

parameter analysis set is defined as all patients who are treated and who have at least 1 of the PK parameters of interest.

CCI

[REDACTED]

- [REDACTED]
- [REDACTED]
- [REDACTED]
- [REDACTED]
- [REDACTED]
- [REDACTED]
- [REDACTED]
- [REDACTED]

5.5. QTc Analysis Set

The QTc analysis set will be defined as all subjects enrolled in the study having at least one ECG assessment after receiving at least one dose of PF-04449913 or azacitidine. This will be the primary set for the ECG analysis. All ECGs obtained during the study will be evaluated for safety. ECG collected prior to the first day of dosing will be considered the baseline ECG.

The evaluable set for the purpose of QTc vs. concentration analysis will be defined as all subjects enrolled in the study as described above and also having at least one matched PK assessment (not different between the ECG and PK assessment by greater than 10% of the half-life). This will be the primary set for evaluating all of the planned ECG and PK assessments.

5.6. Treatment Misallocations

Patients' treatment arm assignment is allocated with an Interactive Response Technology (IRT) system for both the safety LIC and the expansion component of the study. Patients will be analyzed in the arm they are treated.

5.7. Protocol Deviations

A major deviation in the safety LIC and expansion component of the study includes, but is not limited to, treatment misallocation.

6. ENDPOINTS AND COVARIATES

6.1. Efficacy Endpoint(s)

For this study there are two different types of efficacy endpoints:

- Response-related endpoints
- Time to event endpoints

CCI [REDACTED]

6.1.1. Response endpoint

- **CR rate**

Primary endpoint for the expansion component of the study is proportion of patients achieving CR. Of note a confirmation of response (Peripheral Blood only) is required 4 weeks after the first assessment per IWG 2006 for MDS patients.

- **Response Rate**

Response rate (percentage of patients achieving CR + PR) is defined by modified IWG criteria (2006) (Appendix 2).

Of note a confirmation of response (Peripheral Blood only) is required 4 weeks after the first assessment per IWG 2006 for MDS patients.

- CCI [REDACTED]

6.1.2. Response-related endpoints disease-specific

6.1.2.1.1. AML Cohort

Hematologic Responses

- CR, for AML also named as Complete Response
- Complete Remission with partial hematologic recovery (CRh)
- CR with incomplete Blood Recovery (CRi)
- Morphologic Leukemia-Free State (MLFS)
- Partial Remission (PR)
- Stable Disease (SD)

Cytogenetics Responses

- Cytogenetic Complete Response (CRc)
- Molecular Complete Response (CRm)

CCI

6.1.2.1.2. MDS Cohort

Hematologic Responses

- CR
- PR,
- marrow CR (mCR)
- SD
- Complete or Partial Cytogenetic Response

Hematologic Improvement (HI):

HI (defined only for MDS patients) is derived based on hematology lab and RBC transfusion data according to criteria detailed in Appendix 2.

Of note that HI for neutrophils improvement obtained within 3 weeks of the last administration of growth factors (GCSF/GM-CSF) is considered not evaluable. Additionally, HI for erythroid improvement obtained within one week of the last administration of transfusion of red blood cell is considered not evaluable, and HI for platelets improvement obtained within 3 days of the last administration of transfusion of platelets is considered not evaluable.

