Proposed modified IWG Myelodysplasia Response Criteria for Hematologic Improvement (HI)**

[figure not shown]
Erythroid response (pre-treatment <11g/dL)*	Hgb increase by ≥ 1.5 g/dL Relevant reduction of units of RBC transfusions by an absolute number of at least 4 RBC transfusions/8 weeks as compared to the pretreatment transfusion number in the previous 8 weeks (only RBC transfusions given for Hb ≤ 9 g/dL pretreatment will count in the RBC transfusion evaluation).
Platelet Response (pretreatment <100 x10 ⁹ /L)*	Absolute increase of ≥ 30 x10 ⁹ /L if starting with >20 x 10 ⁹ /L platelets Increase from <20 x 10 ⁹ /L to >20 x10 ⁹ /L and by at least 100%
Neutrophil Response (pretreatment <1 x 10 ⁹ /L)*	At least a 100% increase and an absolute increase >0.5 x10 ⁹ /L
Progression or relapse after HI in the absence of another explanation	At least one of the following: 
 • At least 50% decrease from maximum response levels in granulocytes or platelets; • Reduction in Hgb by ≥ 1.5g/dL; • Transfusion dependence.

*Pretreatment counts averages of at least 2 measurements (not influenced by transfusions) ≥ 1 week apart.

** Hematologic Improvement must last ≥ 8 weeks and is derived based on lab data entered in the database.

***This criteria will be applied to MDS patients enrolled in the Safety Lead-In and Expansion components of the study and patients with oligoblastic AML and CMML without proliferative disorder enrolled into the Safety Lead-In component of the study.

Appendix 3. Myelodysplastic Syndromes: 2014 Update on Diagnosis, Risk-Stratification, and Management*

* Applies to MDS patients enrolled in the Safety Lead-In and Expansion components of the study and patients with AML with 20-30% blasts and multi-lineage dysplasia and CMML without proliferative disorder enrolled into the Safety Lead-In component of the study.

Source: Schanz J, Tüchler H, et al. New comprehensive cytogenetic scoring system for primary myelodysplastic syndromes (MDS) and oligoblastic acute myeloid leukemia after MDS derived from an international database merge. J Clin Onc 2012; 30:820-29.

Figure from Garcia-Manero G. Myelodysplastic syndromes: 2014 update on diagnosis, risk stratification, and management. American Journal of Hematology 2014; 89(1):97-108.

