7.2. Efficacy Analysis

For primary and secondary efficacy analyses, no values will be imputed for missing data. Censoring for time-to-event endpoints are defined in [Section 6.1](#). In the assessment of response (at interim or final analysis), patients who are not known to have achieved response will be counted as non-responders.

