8.2.2.2.2. Other Efficacy Measures

Specifically, for AML cohort, the following binary efficacy endpoints (with 95% exact CI) will be summarized in frequency tables, proportion of patients achieving CR, CRh, CRi, CR/CRi, MLFS, PR, SD, CRc, , CRm, and CR+PR.

For MDS cohort, the following binary efficacy endpoints (with 95% exact CI) will be summarized in frequency tables, proportion of patients achieving CR, marrow CR, PR, SD, CR+PR, and Partial or Complete Cytogenetic Response, as well as the proportion of patients ever achieving HI.

The FAS will be used.

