Appendix 2. IWG Criteria: Response Criteria and Progression Definitions for Myelodysplasia***

Response Criteria (responses CR, PR, mCR must last at least 4 weeks)	Peripheral Blood				Bone Marrow Blasts (BMB) (%)	Other
	Hgb(g/dL)	Neutrophils (L)	Platelets (L)	Blasts (%)		
Complete Remission (CR)**	≥11	≥1 x 10 ⁹	≥100 x 10 ⁹	0	≤5	Normal maturation of all cell lines, note if has persistent dysplasia
Partial Remission (PR)**					Decreased by ≥50% but still >5%	All CR criteria if abnormal before treatment except BMB
Marrow CR (mCR)	If hematologic improvement (HI) response, note in addition to Marrow CR				≤5% & decreased by ≥50%	
Stable Disease*						Failure to achieve PR & no evidence of progression*
Failure						Death, or disease progression: worsening cytopenia, increase in % BM blasts, progression to a more advanced MDS FAB subtype
Relapse after (m)CR or PR					ICH	At least one of the following: Return to pre-treatment BMB % Decrement of ≥50% from maximum remission/response levels in granulocytes or platelets Reduction in Hgb ≥1.5g/dL or transfusion dependence

Additional Response Criteria for Myelodysplasia

Cytogenetic Response	
Complete	Disappearance of chromosomal abnormality with no appearance of new ones
Partial	≥50% reduction of chromosomal abnormality
Disease Progression For patients with % blasts at screening: <5% bone marrow blasts 5-10% bone marrow blasts 11-20% bone marrow blasts 21-30% bone marrow blasts	≥50% increase to >5% bone marrow blasts ≥50% increase to >10% bone marrow blasts ≥50% increase to >20% bone marrow blasts ≥50% increase to >30% bone marrow blasts
For all categories, any of:	At least 50% decrease from maximum remission/response in granulocytes or platelets Reduction in Hgb by ≥2 g/dL Transfusion dependence

Proposed modified IWG Myelodysplasia Response Criteria for Hematologic Improvement (HI)**

Erythroid response (pre-treatment <11g/dL)*	Hgb increase by ≥1.5 g/dL Relevant reduction of units of RBC transfusions by an absolute number of at least 4 RBC transfusions/8 weeks as compared to the pretreatment transfusion number in the previous 8 weeks (only RBC transfusions given for Hb ≤9 g/dL pretreatment will count in the RBC transfusion evaluation).
Platelet Response (pretreatment <100 x10 ⁹ /L)*	Absolute increase of ≥30 x10 ⁹ /L if starting with >20 x 10 ⁹ /L platelets Increase from <20 x 10 ⁹ /L to >20 x10 ⁹ /L and by at least 100%

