Neutrophil Response (pretreatment <1 x 10 ⁹ /L)*	At least a 100% increase and an absolute increase >0.5 x10 ⁹ /L
Progression or relapse after HI in the absence of another explanation	At least one of the following: 
 • At least 50% decrease from maximum response levels in granulocytes or platelets; • Reduction in Hgb by ≥1.5g/dL; • Transfusion dependence.

*Pretreatment counts averages of at least 2 measurements (not influenced by transfusions) ≥1 week apart.

** Hematologic Improvement must last ≥ 8 weeks and is derived based on lab data entered in the database.

***This criteria will be applied also to patients with oligoblastic AML and CMML without proliferative disorder.

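### The SAP's one-week red-cell exclusion is not limited to the hemoglobin criterion, so it can void erythroid HI met by transfusion reduction

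*SAP*

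**What the plan says.** SAP 6.1.2.1.2 (MDS Cohort) says that HI "is derived based on hematology lab and RBC transfusion data according to criteria detailed in Appendix 2". It then sets three exclusions by lineage. The red-cell one reads: "HI for erythroid improvement obtained within one week of the last administration of transfusion of red blood cell is considered not evaluable". It has no exception for either erythroid criterion.

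SAP Appendix 2 lists two erythroid criteria. One is a laboratory change: "Hgb increase by ≥1.5 g/dL". The other is a count: "Relevant reduction of units of RBC transfusions by an absolute number of at least 4 RBC transfusions/8 weeks", compared with the 8 weeks before treatment. Protocol Appendix 2 carries the same count criterion ("by an absolute number of at least 4 RBC transfusions/8 weeks as compared to the pretreatment transfusion number in the previous 8 weeks") and attaches no one-week rule to it.

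Three other provisions matter:

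- **Duration** (SAP Appendix 2, footnote): "Hematologic Improvement must last ≥ 8 weeks and is derived based on lab data entered in the database".
- **Scoring** (SAP 8.2.2.2.2): the MDS expansion reports "as well as the proportion of patients ever achieving HI", on the full analysis set. SAP 8.2.2.1.2 also reports HI as ever achieved for MDS patients in the lead-in cohort.
- **Missing response** (SAP 7.2): "patients who are not known to have achieved response will be counted as non-responders".

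**The concern.** The two erythroid criteria need different protection. A recent transfusion raises hemoglobin directly, so a washout before a hemoglobin reading makes sense. The transfusion-reduction criterion is a count over 8 weeks, in which each transfusion is already part of the quantity measured. It does not require transfusion independence: a patient who falls from 12 to 6 units per 8 weeks meets it while still being transfused. Under the sentence as written, whether that response is evaluable depends on how many days have passed since the last unit, which says nothing about whether the count fell.

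The error runs one way. A voided response can only move a patient from responder to non-responder, and that patient stays in the denominator. HI is a named secondary endpoint for the MDS expansion (Protocol 2.4), where improvement in transfusion need is part of what is being measured.

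**Working it through.** The documents state no HI rate and no HI sample size, so there is no plan figure to reproduce. The check compares the rule with the criterion, then asks how often the rule would apply.

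**Inputs from the documents.** Exclusion window 7 days (SAP 6.1.2.1.2). Counting window 8 weeks = 56 days, minimum reduction 4, minimum duration 8 weeks (SAP Appendix 2). Day 1 hematology in each 28-day cycle from Cycle 2 (Protocol Table 3). About 30 MDS patients (Protocol 9.1.2).

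**Inputs assumed.** The number of residual transfusion visits per 8 weeks, *k*, and their timing. Neither document gives a distribution of transfusion burden. In the example above, 6 residual units given two at a time is *k* = 3.

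**Step 1. One date, even spacing.** The interval between visits is 56/*k* days, so the share of dates within 7 days after a transfusion is min(1, 7*k*/56):

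- *k* = 2: 7/28 = 25%
- *k* = 3: 7/18.7 = 37.5%, about 38%
- *k* = 4: 7/14 = 50%
- *k* = 8: 7/7 = 100%

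Counting one transfusion per visit, *k* = 8 needs a baseline of at least 8 + 4 = 12 per 8 weeks.

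**Step 2. One date, random timing.** The probability that a date is voided is 1 − (49/56)^*k*: 23% (*k* = 2), 33% (*k* = 3), 41% (*k* = 4) and 66% (*k* = 8).

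**Step 3. Ever achieved.** One evaluable date is enough, so the patient-level question is whether all dates are voided. A simulation (20,000 runs per setting, transfusions placed at random, assessments 28 days apart) gave:

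| *k* | All of 3 dates voided | All of 6 dates voided |
|---|---|---|
| 2 | 0.6% | 0.0% |
| 3 | 2.8% | 0.06% |
| 4 | 5.0% | 0.2% |
| 8 | 24.9% | 5.5% |

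This gain depends on transfusion dates not running in step with visits. With a fixed 14-day interval, 28 = 2 × 14, so each Day 1 visit falls at the same point between transfusions and repeated visits add nothing unless HI is also evaluated on other dates.

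**Step 4. Rule applied throughout the response.** If every date in the required 8 weeks had to be more than 7 days after a transfusion, any *k* ≥ 1 would fail, and the criterion would be closed to everyone still transfused. The SAP neither states nor excludes this reading. It also does not say on which date HI by transfusion reduction is obtained.

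**Step 5. Effect on the reported rate.** With 30 patients, each one misclassified lowers the HI proportion by 1/30 = 3.3 percentage points.

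**The case against.** The strongest reply is that the sentence was meant only for laboratory values. It stands in a series of three washouts (growth factor for neutrophils, red cells for the erythroid lineage, platelets for platelets), each of which fits a blood count inflated by recent support. The same section says that transfusion data are used, so the 8-week count remains in force. On that view this is loose drafting. The intention is plausible, but the text does not say so: the exclusion covers erythroid improvement as a whole, and the erythroid lineage is the only one of the three with a transfusion-count criterion. Two programmers following the SAP could report different HI rates from the same data.

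A reader might also infer that the rule blocks the transfusion-reduction criterion for anyone still transfused, or that 25% to 50% of such responders would be lost. The documents support neither. The rule voids improvement obtained within a week of a transfusion, not improvement in every transfused patient. The percentages describe one assessment date, while the endpoint needs only one qualifying date on study. A patient with one voided date and a later evaluable one is known to have responded, so SAP 7.2 does not count that patient as a failure.

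It is also true that HI is one of several descriptive secondary measures, in a study with no formal hypotheses (SAP 4.1). That limits the consequence but does not reconcile the two passages.

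**Conclusion.** The concern holds in a limited form. The one-week exclusion is not confined to the hemoglobin criterion, so it can void erythroid HI met by transfusion reduction in MDS patients who still receive some transfusions. Patients left with no evaluable date count as non-responders, which biases the HI rate downward.

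The size cannot be fixed from the documents. The 25%, 38% and 50% figures at 2, 3 and 4 residual visits are single-date probabilities under even spacing. Under random timing, the patient-level loss over three assessments 28 days apart is about 0.6%, 2.8% and 5.0%. Every date is lost only when transfusions are about weekly or more frequent, or if the rule is applied throughout the required 8 weeks, which the SAP leaves open. The reasoning takes the two erythroid entries in Appendix 2 as alternatives; the extracted table shows no connecting word.

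The primary CR analysis and the futility rule do not use HI and are unaffected.

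**What to change.** Amend SAP 6.1.2.1.2 in three respects:

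1. Apply the one-week red-cell exclusion only to the hemoglobin-increase criterion.
2. Evaluate the transfusion-reduction criterion on the red-cell unit count over the 8-week window against the 8 weeks before treatment, regardless of the date of the last transfusion.
3. Take HI by that criterion as obtained on the date a qualifying 8-week window is complete. Without this, the date stays undefined even after the exclusion is narrowed.

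The cost is a sentence or two in the SAP and the matching derivation code. No new data are needed: transfusion dates, unit counts and the 8-week history before screening are already recorded (Protocol 7.4 and Table 3, footnote 20). The protocol's response criteria need no change.
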